Heart Failure Medication Study

Version: 6

Date: July 19, 2018

NCT Number: NCT03402750

1) Protocol Title

Heart Failure Medication Study

2) Objectives*

The objective of this investigation is to pilot test a medication in-hand intervention (Meds to Beds) compared to standard care for patients with heart failure (ICD-50[all numbers]). We expect the intervention to improve adherence and physical health, and reduce hospital re-admissions. We also expect the study to provide evidence for the feasibility and acceptability of the medication-in-hand intervention.

3) Background*

Heart failure is a chronic disease that increases mortality, reduces quality of life, and increases health care system costs. About 6.5 million people in the United States and 26 million worldwide have heart failure. Heart failure patients face many barriers to adherence to their medication regimen, including being prescribed an average of 6.4 medications daily. Promoting continuity of care in regard to prescription medication from the bedside with a medication in-hand intervention (Meds to Beds) may therefore help patients with heart failure improve adherence to medications, and thus improve health.

4) Inclusion and Exclusion Criteria*

Primary inclusion criterion is an admission diagnosis of heart failure ICD-50, including I50.1, I50.2, I50.20, I50.21, I50.22, I50.23, I50.3, I50.30, I50.31, I50.32, I50.33, I50.4, I50.40, I50.41, I50.42, I50.43, I50.8, I50.81, I50.810, I50.811, I50.812, I50.813, I50.814, I50.82, I50.83, I50.84, I50.89, I50.9, or any combination thereof.

To be included patients must also be:

1. age 18 or older;
2. in New York Heart Association Heart Failure Class II or Class III, with ejection fraction below 45%;
3. Cognitively intact, without significant psychological impairment affecting medication adherence such as dementia noted in patient record.

Exclusion criteria are:

1. Patients with medical conditions, such as active cancer or pregnancy, expected to alter heart failure medication management;
2. Patients discharged to nursing homes or hospice care, as they may not be responsible for their own adherence;
3. Prisoners and those unable to provide a point of contact for follow-up assessment;
4. Patients who do not plan to fill discharge medications at the Jackson Memorial Hospital pharmacy.

5) Procedures Involved*

Participants will be identified and recruited from inpatient units at Jackson Memorial Hospital using the electronic health record. At consent, participants will be asked to sign a HIPAA waiver to allow access to their medical record for 60 days after discharge. 60 participants will be randomly assigned to one of two intervention conditions: 1) Meds to Beds, patients receive medication in-hand at discharge from the hospital, and 2) standard care (patient pickup at the pharmacy) comparison group. Adherence to medication will be measured with 1) self-report Adherence to Refills and Medications Scale (ARMS), and 2) pharmacy refill data. Health will be assessed with the self-report PROMIS 10, a measure developed by researchers for patient-reported evaluation of global health. Information on hospital readmission, other hospital visits, and deaths will be obtained from the electronic health record. Feasibility will be determined by tracking the number of patients who receive medications before discharge in the Meds to Beds intervention and by asking patients at follow-up how they received their discharge medications and about their experiences with healthcare. Acceptability will be assessed with 2 questions created for this study. A self-report questionnaire with 7 items created for this study will assess theoretical mechanisms of change for the Meds to Beds intervention. Self-report measures will be administered in-person before randomization, and/or about 30 days post-discharge by telephone or in-person. Prescription refill and other information from the electronic health record will be monitored for up to 60 days post-baseline in order to collect data about the period 30 days post-discharge. Measures are either available in English and Spanish from the authors, or will be translated using a translation back-translation approach.

6) Data and Specimen Banking*

There will be no specimen banking.

7) Data Management*

Protection of patient privacy and confidentiality will be maintained in highest priority at all times. All files will be kept in a locked office and data stored on a secured drive. All personally identifying patient information will be kept separate from patient data at all times.

8) Risks to Subjects*

This study is expected to be of minimal risk to participants. Special care will be taken to ensure patients do not confuse participation in this study with their treatment plan, and continue to contact their regular providers for any issues or questions regarding their medication or health.

9) Potential Benefits to Subjects*

This study provides no direct benefit to participants.

10) Vulnerable Populations*

This study will not include pregnant women, prisoners, children or cognitively impaired adults.

11) Setting

Some study data will be collected at inpatient units at Jackson Memorial Hospital, with follow-up via telephone or in-person with these participants.

12) Resources Available

[name], BSN, RN, PhD is a fourth-year doctoral student in Nursing at the University of Miami School of Nursing and Health Studies. She has spent the past three years researching cardiovascular disease and medication adherence, including a participating in graduate-level nursing clinical at Jackson Memorial Hospital. She is fully bilingual in English and Spanish, and will be responsible for all data collection.

13) Prior Approvals

Approval of Jackson Memorial Hospital will be obtained before commencing this study.

14) Recruitment Methods

A partial HIPAA waiver will be requested to identify patients admitted to Jackson Memorial Hospital with a heart failure diagnosis who may qualify for the investigation. These patients will be approached at bedside by a known person such as a nurse or physician and invited to participate in the study. If interested in participating patients will be screened by researcher with a preliminary questionnaire regarding medical history and contact information. Qualifying patients will be asked to sign a consent form. At the time of inclusion in the study, participants will receive a gift card worth \$20 as compensation. In addition, participants will receive \$50 as compensation for completing the telephone follow-up portion of the study.

15) Local Number of Subjects

There will be up to 60 participants (30 Meds to Beds, 30 standard care).

16) Confidentiality

Patient confidentiality will be maintained at all times; they will only be contacted by one researcher. Data and responses will be linked using a numerical ID; a linking list with names matched to ID will be stored separately from data by the principal investigator in secure location.

IRB Study Number: HRP-503 20160741

Version #6 July 19, 2018

No specimen samples will be taken, used or stored in this investigation.

17) Provisions to Protect the Privacy Interests of Subjects

One researcher will be responsible for the screening, consent process and interviews of participants to limit intrusion of privacy.

18) Consent Process

Potential participants will be approached at Jackson Memorial Hospital after identification in the medical record.

Only patients with qualifying diagnoses identified by physicians as stable for participation in the research study will be approached after an introduction by a “known individual” (such as a nurse or doctor).

The study PI is fluent in English and Spanish, and will recruit English- and Spanish-speaking participants for the study. All informational and consent material will be available in English and Spanish.

There will be no individuals under age 18 included in the study.

19) Process to Document Consent in Writing

Potential participants will be approached and informed of potential eligibility to enroll in the study. If the participants agree, they will be explained the risks and benefits of being involved in the study. They will be asked several screening questions to confirm eligibility. Participants who are eligible and wish to enroll in the study will be provided the consent form and any questions or concerns will be answered and addressed. A copy of the signed and dated consent form will be provided to the participant.

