Statistical Analysis Plan

Heart Failure Medication Adherence

Date: July 19, 2018

Version: 1

NCT Number: NCT03402750

Data Analysis Plan

Statistical Assumptions. It is necessary to confirm the assumptions of the statistical tests that will be used in this study (ANOVA, repeated measures ANOVA, and chi-square). For repeated measures ANOVA, the assumptions are multivariate normality (a normal distribution to higher dimensions), homogeneity of the covariance matrices (that these be similar across groups), and independence of the variables. Multivariate normality will be tested using Mardia's multivariate kurtosis (Yuan, Lambert & Fouladi, 2004). Homogeneity of the covariance matrices will be tested with Mauchly's sphericity test (Mauchly, 1940). There is no statistical test for independence, but the randomized design of the study supports this assumption. ANOVA has similar assumptions, which will also be tested. Chi-square will be used if assumptions are violated. For the chi-square test, the assumptions are that the data is categorical and that the groups are independent. These assumptions will be met as a result of the study design and appropriate sample size.

Hypotheses

Hypothesis 1. Participants in the intervention group will have better medication adherence than the control group.

Hypothesis 1A. Medication adherence (calculated with medication possession ratio) of participants in the intervention group will be higher than those in the control group at 30 days.

Hypothesis 1B. Self-reported medication adherence among participants in the intervention group will be higher than those in the control group at 30 days.

These hypotheses will be tested using ANOVA.

Hypothesis 2. The Meds to Bed intervention will have strong feasibility and acceptability.

Hypothesis 2A: The Meds to Beds intervention will have at least 90% successful deliveries of medication before discharge.

Hypothesis 2B: Participants in the Meds to Beds condition will report a better experience obtaining hospital discharge medications than those in the control group.

Hypothesis 2C: Participants in the Meds to Beds condition will report a better experience overall in the study than those in the control group.

Hypothesis 2A will be tested with a proportion in the intervention condition. Hypotheses 2B and 2C will be tested using ANOVA.

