Hypothesis 3. Participants in the intervention group will have lower deterioration in physical health from baseline to 30 days after discharge than the control group.

This hypothesis will be tested using repeated measures ANOVA.

Hypothesis 4. Participants in the intervention group will have a lower proportion of readmissions and deaths than the control group.

Hypothesis 4A. The intervention group will have a lower proportion of readmissions at 30 days than the control group.

Hypothesis 4B. The intervention group will have a lower proportion of deaths at 30 days than the control group.

These hypotheses will be tested using a chi-square test.

Hypothesis 5. Participants in the intervention group will have lower increases in mechanisms of action variables 30 days after discharge than the control group.

Hypothesis 5A. The average length of time (in 0-30 days) before beginning a prescription medication regimen for participants in the intervention group will be lower than among those in the control group.

Hypothesis 5B. Participants in the intervention group will report lower increases in Personal Inconvenience (*Patient Factor* of belief that medications will be difficult to obtain) than those in the control group.

Hypothesis 5C. Participants in the intervention group will report a higher score in in Immediacy of Benefit (*Therapy-related factor*) than those in the control group.

Hypothesis 5D. Participants in the intervention group will report lower increases in Fatigue (*Condition-related Factor*) than those in the control group.

Hypothesis 5E. Participants in the intervention group will report lower increases in Family Inconvenience (*Social/economic factor* of reduced family support) than those in the control group.

Hypothesis 5F. Participants in the intervention group will report lower increases in Prescription-related Paperwork (*Health care team / health system factor*) than those in the control group.

Hypotheses 5A-5F will be tested using ANOVA or repeated measures ANOVA, depending on the number of times the outcome is assessed.

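### The protocol does not guarantee a pre-randomisation ARMS or mechanism score, so H1B gives up precision and the change hypotheses H5B, D, E and F rest on a schedule that has to be inferred

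*Protocol*

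**What the plan says.** Protocol section 5 (Procedures Involved) times the self-report measures as a group: "Self-report measures will be administered in-person before randomization, and/or about 30 days post-discharge by telephone or in-person". Neither document contains a schedule of assessments that allocates each instrument to a visit. The two instruments at issue are introduced in the same section with no time attached: "Adherence to medication will be measured with 1) self-report Adherence to Refills and Medications Scale (ARMS), and 2) pharmacy refill data" and "A self-report questionnaire with 7 items created for this study will assess theoretical mechanisms of change for the Meds to Beds intervention". Only the questions on how discharge medicines were received and on healthcare experience are tied there to follow-up.

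In the SAP, H1B reads "Self-reported medication adherence among participants in the intervention group will be higher than those in the control group at 30 days", and the test for H1A and H1B is given as "These hypotheses will be tested using ANOVA". No covariate or repeated measure is named. H3 is different: it concerns "lower deterioration in physical health from baseline to 30 days after discharge than the control group" and is assigned repeated measures ANOVA, so a baseline for the health measure is clearly intended.

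H5B reads "Participants in the intervention group will report lower increases in Personal Inconvenience". H5D, H5E and H5F have the same form for fatigue, family inconvenience and paperwork. H5A is a number of days and H5C a higher score. One sentence covers all six: "Hypotheses 5A-5F will be tested using ANOVA or repeated measures ANOVA, depending on the number of times the outcome is assessed".

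Protocol section 15 gives the size: up to 60 participants, 30 per arm.

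**The concern.** There are two separate consequences.

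First, H1B. A baseline ARMS score may not be collected, and if it is, the stated test does not use it. Where pre-admission adherence predicts adherence at 30 days, a baseline covariate removes part of the between-patient variation. In a trial of at most 60 patients that is worth having. A score not taken before randomisation cannot be recovered later.

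Second, H5B, D, E and F. A claim that something rose less in one arm needs a value before and a value after. If an item is asked only at 30 days, the analysis compares levels and cannot support the hypothesis as worded. The protocol leaves the number of assessments open, and the SAP makes the choice of test depend on that number. Neither document settles it.

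**Working it through.** **Step 1: the texts side by side.**

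| Hypothesis | What it claims | Stated test | Baseline stated? |
|---|---|---|---|
| H1B (ARMS) | level at 30 days | ANOVA | no |
| H3 (physical health) | change, baseline to 30 days | repeated measures ANOVA | yes |
| H5A | days to starting the regimen | ANOVA or repeated measures | not needed |
| H5C | higher score | ANOVA or repeated measures | no |
| H5B, D, E, F | smaller increase | ANOVA or repeated measures | no |

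For H5B, D, E and F the claim requires two assessments and no sentence in either document provides for them explicitly. This part needs no arithmetic.

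**Step 2: inputs for H1B.** From the documents: 30 per arm. The documents give no alpha, sidedness, power, effect size, SD, correlation or dropout, so there is no sample-size calculation to reproduce. Assumed here: two-sided alpha 0.05, 80% power, no dropout, outcome SD of 1, and a correlation r between baseline and 30-day ARMS of 0.3, 0.5 or 0.7. The normal approximation is used.

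**Step 3: 30-day score only.** Detectable difference = (1.960 + 0.842) × sqrt(2/30) = 2.802 × 0.258 = 0.72 SD.

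**Step 4: with baseline as covariate.** The residual SD is multiplied by sqrt(1 − r²), so residual variance falls by r². The equivalent unadjusted total is 60/(1 − r²).

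| r | Variance cut (r²) | Detectable difference | Equivalent unadjusted total | Power for 0.5 SD |
|---|---|---|---|---|
| no baseline | – | 0.72 SD | 60 | 49% |
| 0.3 | 9% | 0.72 × 0.954 = 0.69 SD | 66 | 53% |
| 0.5 | 25% | 0.72 × 0.866 = 0.63 SD | 80 | 61% |
| 0.7 | 49% | 0.72 × 0.714 = 0.52 SD | 118 | 77% |

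(Products use the unrounded 0.7234.)

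**Step 5: why a covariate and not a change score for H1B.** A change score multiplies the SD by sqrt(2(1 − r)). The detectable differences are then 0.86, 0.72 and 0.56 SD at r = 0.3, 0.5 and 0.7. That is worse than no baseline at r = 0.3, equal at 0.5, and behind the covariate throughout.

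**Step 6: chance imbalance.** The baseline difference between arms has standard deviation sqrt(2/30) = 0.26 SD and exceeds 0.25 SD in one direction or the other with probability about 33%. This is not an error on top of Step 3. Whatever part carries through to 30 days is already inside the standard error of the unadjusted comparison.

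**The case against.** The strongest reply is that the wording is loose but the intent is clear. The phrase *and/or* covers a mixed set: PROMIS 10 must be taken twice for H3, while discharge-medication experience can only be asked afterwards. The single H5 sentence likewise covers outcomes of different kinds. A time to starting treatment is measured once, so ANOVA has to be on offer. The natural reading is ANOVA for H5A, perhaps H5C, and repeated measures for the four change hypotheses. This largely stands: repeated measures is the likely intent. What remains is that a reader has to infer it.

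On H1B, the reply is that the hypothesis is about a level at 30 days, ANOVA tests exactly that, and randomisation makes the comparison valid. This stands too. The covariate is an improvement in precision, and its size depends on an assumed r; at r = 0.3 the gain is small.

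A reader might go further and infer three things that the documents do not support:

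- That no baseline will be taken. The protocol wording allows both time points.
- That H1B is biased by chance differences in prior adherence. As Step 6 shows, the planned test already allows for these.
- That ARMS must be uncollected at baseline because the SAP does not assign it repeated measures. The rule linking test to number of assessments is written for H5 only; H1 has its own stated test, and a baseline ARMS could still be reported descriptively.

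That this is a pilot lowers the stakes, but the SAP still states directional hypotheses with tests.

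**Conclusion.** The point holds as a gap in specification and a missed gain in precision. A pre-randomisation ARMS or mechanism score is not guaranteed by either document.

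For H1B the planned analysis is valid. Its cost is a detectable difference of 0.72 SD where 0.69 to 0.52 SD would be available with baseline adjustment, over an assumed r of 0.3 to 0.7 and the other assumptions in Step 2. Dropout would enlarge all of these figures.

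For H5B, D, E and F the conclusion rests on the text alone. The hypotheses need two measurements, two are probably intended, and neither document says so. If any of these items were asked once, its hypothesis as worded could not be tested.

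**What to change.** **Protocol section 5.** Replace *and/or* with a measure-by-time schedule:

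- before randomisation and at 30 days: ARMS, PROMIS 10, and the items behind H5B, D, E and F;
- at 30 days only: experience, acceptability and time-to-start items;
- H5C: state its timing explicitly, since it is worded as a score under a general hypothesis about increases.

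**SAP, Hypothesis 1.** Test H1B by ANCOVA on 30-day ARMS with baseline ARMS as covariate. Include an indicator for patients with no medication regimen before admission, so that none is dropped for lack of a baseline score.

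**SAP, Hypothesis 5.** Limit the single-assessment ANOVA to H5A, and to H5C if it is measured once. Analyse H5B, D, E and F with both measurements. Any item that cannot sensibly be answered before discharge should be reworded as a 30-day level.

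**Cost.** The protocol already provides for in-person administration before randomisation, and H3 needs a baseline health score in any case. The added burden is a slightly longer bedside interview, one extra model term for patients new to medication, and the wording changes.

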Statistical Analysis Plan

Heart Failure Medication Adherence

Date: July 19, 2018

Version: 1

NCT Number: NCT03402750

Data Analysis Plan

Statistical Assumptions. It is necessary to confirm the assumptions of the statistical tests that will be used in this study (ANOVA, repeated measures ANOVA, and chi-square). For repeated measures ANOVA, the assumptions are multivariate normality (a normal distribution to higher dimensions), homogeneity of the covariance matrices (that these be similar across groups), and independence of the variables. Multivariate normality will be tested using Mardia's multivariate kurtosis (Yuan, Lambert & Fouladi, 2004). Homogeneity of the covariance matrices will be tested with Mauchly's sphericity test (Mauchly, 1940). There is no statistical test for independence, but the randomized design of the study supports this assumption. ANOVA has similar assumptions, which will also be tested. Chi-square will be used if assumptions are violated. For the chi-square test, the assumptions are that the data is categorical and that the groups are independent. These assumptions will be met as a result of the study design and appropriate sample size.

Hypotheses

Hypothesis 1. Participants in the intervention group will have better medication adherence than the control group.

Hypothesis 1A. Medication adherence (calculated with medication possession ratio) of participants in the intervention group will be higher than those in the control group at 30 days.

Hypothesis 1B. Self-reported medication adherence among participants in the intervention group will be higher than those in the control group at 30 days.

These hypotheses will be tested using ANOVA.

Hypothesis 2. The Meds to Bed intervention will have strong feasibility and acceptability.

Hypothesis 2A: The Meds to Beds intervention will have at least 90% successful deliveries of medication before discharge.

Hypothesis 2B: Participants in the Meds to Beds condition will report a better experience obtaining hospital discharge medications than those in the control group.

Hypothesis 2C: Participants in the Meds to Beds condition will report a better experience overall in the study than those in the control group.

Hypothesis 2A will be tested with a proportion in the intervention condition. Hypotheses 2B and 2C will be tested using ANOVA.

Hypothesis 3. Participants in the intervention group will have lower deterioration in physical health from baseline to 30 days after discharge than the control group.

This hypothesis will be tested using repeated measures ANOVA.

Hypothesis 4. Participants in the intervention group will have a lower proportion of readmissions and deaths than the control group.

Hypothesis 4A. The intervention group will have a lower proportion of readmissions at 30 days than the control group.

Hypothesis 4B. The intervention group will have a lower proportion of deaths at 30 days than the control group.

These hypotheses will be tested using a chi-square test.

Hypothesis 5. Participants in the intervention group will have lower increases in mechanisms of action variables 30 days after discharge than the control group.

Hypothesis 5A. The average length of time (in 0-30 days) before beginning a prescription medication regimen for participants in the intervention group will be lower than among those in the control group.

Hypothesis 5B. Participants in the intervention group will report lower increases in Personal Inconvenience (*Patient Factor* of belief that medications will be difficult to obtain) than those in the control group.

Hypothesis 5C. Participants in the intervention group will report a higher score in in Immediacy of Benefit (*Therapy-related factor*) than those in the control group.

Hypothesis 5D. Participants in the intervention group will report lower increases in Fatigue (*Condition-related Factor*) than those in the control group.

Hypothesis 5E. Participants in the intervention group will report lower increases in Family Inconvenience (*Social/economic factor* of reduced family support) than those in the control group.

Hypothesis 5F. Participants in the intervention group will report lower increases in Prescription-related Paperwork (*Health care team / health system factor*) than those in the control group.

Hypotheses 5A-5F will be tested using ANOVA or repeated measures ANOVA, depending on the number of times the outcome is assessed.

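### The SAP checks that covariance matrices match across arms with Mauchly's test, which compares no arms and has 0 df with two occasions

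*SAP*

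**What the plan says.** The Statistical Assumptions paragraph of the SAP lists what repeated measures ANOVA needs, including "homogeneity of the covariance matrices (that these be similar across groups". Two sentences later it names the check: "Homogeneity of the covariance matrices will be tested with Mauchly's sphericity test". The same paragraph gives the consequence of a failed check: "Chi-square will be used if assumptions are violated". It says the similar assumptions of ANOVA will also be tested but names no test for them, so the SAP contains no named between-arm comparison of spread.

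The check applies to these analyses:

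- **Hypothesis 3** concerns "lower deterioration in physical health from baseline to 30 days after discharge than the control group", and the SAP adds: "This hypothesis will be tested using repeated measures ANOVA".
- **Hypothesis 5** has this rule: "Hypotheses 5A-5F will be tested using ANOVA or repeated measures ANOVA, depending on the number of times the outcome is assessed". Items 5B, 5D, 5E and 5F are worded as increases, for example "Participants in the intervention group will report lower increases in Fatigue", which implies a baseline and a follow-up value.

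Section 5 of the protocol sets the schedule: "Self-report measures will be administered in-person before randomization, and/or about 30 days post-discharge by telephone or in-person". Section 15 plans up to 60 participants, 30 in each arm.

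**The concern.** The assumption and its test do not match. Similarity across groups is a comparison of two covariance matrices, one per arm. Mauchly's test asks whether one matrix, pooled over arms, has a particular structure. Even with many occasions it would not answer the stated question, and with two occasions its usual form has nothing to test.

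Two things could be at stake. Unequal spread between the arms could distort the error rate of the arm-by-time test without the named check showing it. Also, the SAP ties the choice of analysis to its assumption checks. A check that can never fail, or one that fails for an unrelated reason, would steer that choice wrongly.

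**Working it through.** The documents give no figure on this point to reproduce.

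**Inputs from the documents.** Two arms of 30 (protocol section 15); at most two occasions, k = 2 (protocol section 5; SAP Hypothesis 3).

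**Assumed, because the documents state none of them.** Two-sided 5% level, normal data, numbers completing follow-up, between-arm SD ratio, within-person correlation.

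**1. Degrees of freedom.** For p orthonormal contrasts, Mauchly's df = p(p+1)/2 − 1, with p = k − 1.

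- k = 2: p = 1, df = 1×2/2 − 1 = 0.
- k = 3 would give p = 2, df = 2×3/2 − 1 = 2.

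The statistic is W = det(S)/(tr(S)/p)^p, with S the pooled covariance of the contrasts. With p = 1, S is a single variance s, so W = s/s = 1 whatever the data. Simulation agrees: W was 1 in all 20,000 datasets per setting, at SD ratios 1, 1.5 and 2.

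**2. The other reading.** Applied to the raw 2×2 matrix of the two occasions, p = 2 and df = 2×3/2 − 1 = 2. This form tests equal variances and zero correlation across occasions. Rejection rates at 30/30 (20,000 replicates):

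| Within-person correlation | Arms identical | Arm SD ratio 2 |
|---|---|---|
| 0 | 5% | 11% |
| 0.3 | 54% | 56% |
| 0.5 | 97% | 95% |

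It responds mainly to the correlation that any repeated measure is expected to have, not to a difference between arms.

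**3. What a between-arm check would see at 30/30.** Brown-Forsythe on change detects SD ratio 1.5 in about 47% of datasets and ratio 2 in about 90%. Box's M, with df = p(p+1)(g−1)/2 = 2×3×1/2 = 3, rejects in about 5%, 70% and 99% at ratios 1, 1.5 and 2 (correlation 0.5, 4,000 runs).

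**4. Effect on the analysis.** With two occasions, the arm-by-time F test is the square of the pooled-variance t test on change. Compare the true variance of the difference in mean change with what the pooled formula estimates on average, taking SDs of 1 and 2:

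- 30/30: true 1/30 + 4/30 = 0.167; pooled [(29×1 + 29×4)/58]×(2/30) = 2.5×0.0667 = 0.167. They agree.
- 30/20, smaller arm more variable: true 1/30 + 4/20 = 0.233; pooled [(29×1 + 19×4)/48]×(1/30 + 1/20) = 2.1875×0.0833 = 0.182. The variance is understated.
- 30/20, larger arm more variable: true 4/30 + 1/20 = 0.183; pooled [(29×4 + 19×1)/48]×0.0833 = 2.8125×0.0833 = 0.234. The variance is overstated.

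Simulated type I error at the 5% level (400,000 replicates per cell):

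| Completers | SD ratio | More variable arm | Pooled test |
|---|---|---|---|
| 30/30 | 2 | either | 5.2% |
| 27/27 | 2 | either | 5.1% |
| 24/24 | 2 | either | 5.2% |
| 30/27 | 1.5 | smaller | 5.6% |
| 30/24 | 1.25 | smaller | 5.5% |
| 30/24 | 1.5 | smaller | 6.1% |
| 30/24 | 2 | smaller | 6.9% |
| 30/20 | 2 | smaller | 8.4% |
| 30/24 | 2 | larger | 3.8% |
| 30/20 | 2 | larger | 2.9% |

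Welch's test stayed at 4.9–5.1% throughout. If the level were 10%, the pooled test at SD ratio 2 with the smaller arm more variable would give 10.2% (30/30), 12.6% (30/24) and 14.7% (30/20), against 10.0% for Welch.

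**The case against.** The strongest reply is that the error does almost no harm in the trial as planned. With 30 per arm the pooled test is robust to unequal spread, so even a correct check would protect very little. The 8.4% figure needs one arm to lose a third of its participants, the other to lose none, and an SD ratio of 2 in the unfavourable direction. Nothing in the documents predicts that, and the protocol offers telephone follow-up and a $50 payment for completing it. This is a pilot; Hypotheses 1, 2 and 4 are untouched, and that four Hypothesis 5 items are measured twice is inferred from their wording. The smallest repair would be to name a correct between-arm check, whereas Welch's test replaces the named method. The chi-square fallback is a separate weakness.

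Most of this stands, and it is why the point carries low weight. It does not rescue the sentence: no other part of either document supplies a between-arm check. Balanced retention is hoped for, not assured. Welch's test on change estimates the same arm-by-time contrast as the planned analysis and drops only the pooled variance, so it is a modest change. The fallback adds no weight here, because the repeated-measures form of Mauchly's test could never trigger it.

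**Conclusion.** The concern holds, at low severity. The SAP assigns an across-group assumption to a test that compares no groups. On the two-occasion schedule, that test's repeated-measures form has 0 df. This follows from the documents and algebra alone and needs no assumption.

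The size does rest on assumptions. At a two-sided 5% level and SD ratio 2, there is essentially no effect with equal numbers. With uneven completion down to 30/20, error ranges from 2.9% to 8.4%, depending on which arm is more variable. The scope is Hypothesis 3 and the Hypothesis 5 items measured twice (5B, 5D, 5E and 5F on their wording). The one-way ANOVA and chi-square hypotheses are not affected.

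**What to change.** Delete the Mauchly check. For Hypothesis 3 and the twice-measured Hypothesis 5 items, prespecify Welch's unequal-variance test on change from baseline to 30 days by arm. A baseline-adjusted model with robust (HC3) standard errors is an acceptable alternative. If a between-arm check is kept, such as Brown-Forsythe or Levene on change, state that a failure leads to the unequal-variance analysis and not to chi-square.

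The cost is SAP wording, including the method named for those hypotheses. With equal variances, an assumed true difference of 0.736 SD of change and the 5% level, power is:

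| Completers | Pooled | Welch | Adjusted, ordinary errors | Adjusted, HC3 |
|---|---|---|---|---|
| 30/30 | 80.1% | 80.0% | 89.3% | 88.3% |
| 30/24 | 75.0% | 74.8% | 85.9% | 84.6% |
| 30/20 | 70.6% | 70.2% | 81.4% | 79.2% |

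The Welch loss is at most 70.6 − 70.2 = 0.4 points. The adjusted columns assume a baseline correlation of 0.5 (8,000 replicates); HC3 type I error was 4.3–4.7%.

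Routing a failed check to chi-square would cost far more. On a median split of change at 30/30 (an assumed cut, since the SAP names none), power is 67.7% uncorrected, with a type I error of 7.0%, or 46.7% with continuity correction, against 80.0% for Welch.
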